9.3.2 Outcomes definition

As effectiveness outcomes, IS/SE (as combined endpoint and alone), recurrent IS/SE (as combined endpoint) and severe IS will be analyzed while safety outcomes include ICH, fatal bleeding, recurrent hospitalization, kidney failure and AKI. All study outcomes except kidney failure, fatal bleeding and hospitalizations will be defined based on primary hospital discharge diagnoses (ICD-10 GM codes) as defined in Annex 3: Additional information. The event date will be set to the admission date of the respective hospitalization.

Severe IS will be defined according to an approach proposed by Schubert et al. (8) as hospitalization with a primary hospital discharge diagnosis of IS in combination with an OPS (Operationen und Prozedurenschlüssel) code indicating one of the following: intubation, mechanical ventilation or percutaneous endoscopic gastronomy(see Annex 3: Additional information). In addition, IS cases will be considered as severe if the patients died during the respective hospitalization defined as documented death as reason for hospital discharge.

Cases of fatal bleeding will be defined as hospitalization with a primary hospital discharge diagnoses for bleeding with documented death as reason for hospital discharge or within 30 days after hospital discharge. The date of death will be set to the date of hospital discharge or date of disenrollment from the SHI, respectively.

Hospitalizations (in general and for IS/SE) will be considered as recurrent event if there was at least one day between hospital discharge date of the prior and the admission date of the respective hospitalization.

Kidney failure will also be assessed in the outpatient setting defined as verified ambulatory diagnosis for renal failure in combination with a claim for dialysis based on OPS codes and EBM (Einheitlicher Bewertungsmaßstab) codes in the same or following quarter (see Annex 3: Additional information). The event date for cases with renal failure in the outpatient setting will be set to the first documented claim for dialysis in the respective quarter.

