8.2 Secondary objectives

The secondary objectives of this study are:

- To describe the risk of ischemic stroke (IS) and systemic embolism (SE) as combined effectiveness outcome in the overall population of patients with NVAF initiating treatment with individual NOACs (rivaroxaban, apixaban, edoxaban) compared to phenprocoumon
- To describe the risk of intracranial hemorrhage (ICH) as safety outcome in the overall population of patients with NVAF initiating treatment with individual NOACs (rivaroxaban, apixaban, edoxaban) compared to phenprocoumon
- To describe the risk of IS as effectiveness outcome in patients with NVAF (overall population as well as patients with renal impairment) initiating treatment with individual NOACs (rivaroxaban, apixaban, edoxaban) compared to phenprocoumon
- To describe the risk of SE as effectiveness outcome in patients with NVAF (overall population as well as patients with renal impairment) initiating treatment with individual NOACs (rivaroxaban, apixaban, edoxaban) compared to phenprocoumon

- To describe the risk of kidney failure as safety outcome in patients with NVAF (overall population as well as patients with renal impairment) initiating treatment with individual NOACs (rivaroxaban, apixaban, edoxaban) compared to phenprocoumon
- To describe the risk of acute kidney injury (AKI) as safety outcome in patients with NVAF (overall population as well as patients with renal impairment) initiating treatment with individual NOACs (rivaroxaban, apixaban, edoxaban) compared to phenprocoumon
- To describe the risk of fatal bleeding as safety outcome in patients with NVAF (overall population as well as patients with renal impairment) initiating treatment with individual NOACs (rivaroxaban, apixaban, edoxaban) compared to phenprocoumon
- To describe the risk of recurrent hospitalization for any reason as safety outcome in patients with NVAF (overall population as well as patients with renal impairment) initiating treatment with individual NOACs (rivaroxaban, apixaban, edoxaban) compared to phenprocoumon
- To describe the risk of recurrent IS/SE as combined effectiveness outcome patients with NVAF (overall population as well as patients with renal impairment) initiating treatment with individual NOACs (rivaroxaban, apixaban, edoxaban) compared to phenprocoumon

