9.2.3 Exclusion criteria

Patients meeting any of the following exclusion criteria (see Annex 3: Additional information) will be excluded from the analysis:

• A verified ambulatory or primary/ secondary hospital discharge diagnosis of valvular atrial fibrillation in the baseline period;

- A verified ambulatory or primary/ secondary hospital discharge diagnosis indicating pregnancy in the baseline period;
- A verified ambulatory or primary/ secondary hospital discharge diagnosis of a transient cause of atrial fibrillation in the baseline period;
- A verified ambulatory or primary/ secondary hospital discharge diagnosis of venous thromboembolism (VTE) in the previous or same quarter of the index date;
- A claim for hip or knee replacement surgery in the 60 days prior to or on the index date;
- A prescription of heparin or fondaparinux in the 60 days prior to or on the index date;
- A prescription of more than one oral anticoagulant (rivaroxaban, apixaban, edoxaban or phenprocoumon) on the index date;
- A prescription of warfarin or dabigatran in the baseline period or on the index date;
- A verified ambulatory or primary/ secondary hospital discharge diagnosis of end-stage kidney disease or a claim for dialysis in the baseline period;
- Patients receiving an initial dose of rivaroxaban 10 mg/ 2.5 mg or edoxaban 15 mg (these dosages are not indicated for the treatment of NVAF).
- A prescription of contraindicated drug for apixaban or rivaroxaban due to drug interactions (i.e. azole antifungals and HIV protease inhibitors) in the 60 days before or on the index date.

For the main analysis, patients will be followed from the index date until the first diagnosis of the respective outcome event, discontinuation of the index drug, death, end of continuous insurance in the SHI or the end of the study period (31 December 2017), whichever comes first. Patients will be censored in all analyses if they switch to phenprocoumon or another NOAC (including dabigatran), receive a prescription of heparin/ fondaparinux, warfarin, rivaroxaban 10 mg/ 2.5 mg, edoxaban 15mg or a contraindicated drug as defined above. For specific analyses, the end of follow-up may differ as described in 9.3.1.

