9.9 Limitations of the research methods

Although the analysis dataset obtained from the InGef database covers more than 6 million insured members of SHIs all over Germany, representativeness for all phenprocoumon and NOAC users in Germany cannot be guaranteed if differences exist for instance by socioeconomic status or region. However, this will not affect the internal validity of the study results as the objectives of the study are related to relative risks rather than absolute risk estimates. Representativeness of the underlying data is therefore not a requirement.

As our study does not include a review of individual patient files to confirm the occurrence of individual outcomes such as IS and ICH, which for data protection reasons is generally not feasible, case validation is not possible and outcome misclassification cannot be ruled out. Therefore, only primary hospital diagnoses will be used to identify effectiveness and study outcomes to minimize the amount of false-positive case.

The recurrent event analysis for hospitalizations can only take into account those events which are recorded in the claims database. Therefore, patients could have deceased before any hospitalization.

Since no laboratory data and detailed clinical information are available in the InGef database, patients with an estimated glomerular filtration rate of 15-49 mL/min/1.73m², i.e. with an indication for the reduced dose of rivaroxaban, cannot be identified exactly.

With regard to drug usage, it has to be noted that the dispensation the respective drug does not necessarily imply that the patient actually took the medication. Therefore, exposure misclassification is generally possible; however, in case of continuous drug dispensations to the same patient the amount of misclassification is expected to be low.

In addition, unmeasured or residual confounding may affect the study results because several factors associated with the study outcomes cannot be measured adequately in claims data, e.g. laboratory values, physical activity, smoking. laboratory values and over the counter medications such as aspirin.

Patient populations underlying the common comparator can be different in every comparison planned, so that indirect comparisons of individual NOACs via the common comparator cannot be made.

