B01AF02	Apixaban	11376429	Eliquis 2,5 mg Filmtabletten Milinda	Reduced
B01AF02	Apixaban	11376435	Eliquis 2,5 mg Filmtabletten Milinda	Reduced
B01AF02	Apixaban	11376441	Eliquis 5 mg Filmtabletten Milinda	Standard
B01AF02	Apixaban	11376458	Eliquis 5 mg Filmtabletten Milinda	Standard
B01AF02	Apixaban	11524829	Eliquis 5 mg Axicorp	Standard
B01AF02	Apixaban	11524841	Eliquis 5 mg Axicorp	Standard
B01AF02	Apixaban	13578924	Eliquis 2,5 mg Axicorp	Reduced
B01AF03	Edoxaban	10714031	Lixiana 30 mg Filmtabletten	Reduced
B01AF03	Edoxaban	10714060	Lixiana 30 mg Filmtabletten	Reduced
B01AF03	Edoxaban	10714083	Lixiana 30 mg Filmtabletten	Reduced
B01AF03	Edoxaban	10714143	Lixiana 30 mg Filmtabletten	Reduced
B01AF03	Edoxaban	10714172	Lixiana 60 mg Filmtabletten	Standard
B01AF03	Edoxaban	10714255	Lixiana 60 mg Filmtabletten	Standard
B01AF03	Edoxaban	10714284	Lixiana 60 mg Filmtabletten	Standard
B01AF03	Edoxaban	10714309	Lixiana 60 mg Filmtabletten	Standard

B01AF03	Edoxaban	12749950	Lixiana 30 mg Axicorp	Reduced
B01AF03	Edoxaban	12749967	Lixiana 30 mg Axicorp	Reduced
B01AF03	Edoxaban	12749996	Lixiana 60 mg Axicorp	Standard
B01AF03	Edoxaban	12750002	Lixiana 60 mg Axicorp	Standard
B01AF03	Edoxaban	13695860	Lixiana 30 mg Kohl Ph.	Reduced
B01AF03	Edoxaban	13695877	Lixiana 60 mg Kohl Ph.	Standard

Section 9.3.2. Outcome definition

- Ischemic stroke (IS): ICD-GM: I63
- Severe ischemic stroke according to (8):

ICD-GM: I63 in combination with

OPS: 870, 871 (intubation/mechanical ventilation), 5431, 8017, 8018, 8123 (percutaneous endoscopic gastrostomy)

• Systemic embolism (SE):

ICD-GM: I74

- Intracranial hemorrhage (ICH): ICD-GM: I60 – I62
- Acute kidney injury (AKI) according to (14): ICD-GM: N17
- Kidney failure:

ICD-GM (hospital): N18.5, Z94.0

ICD-GM (ambulatory): N18.5, N18.9, N19, Z94.0 in combination with

OPS: 8853, 8854, 8855, 8857 OR

EBM: (**valid from Q1 2013 onwards**) 13602, 13610, 13611, 40815, 40816, 40817, 40818, 40819,40823, 40824, 40825, 40826, 40827, 40828, 40829, 40830, 40831, 40832, 40833, 40834, 40835, 40836, 40837, 40838

• Fatal bleeding:

OPS: 8800

ICD-GM: D62, H11.3, H21.0, H31.3, H35.6, H43.1, H45.0, H92.2, I32.1, I60, I61, I62, I85.0, J94.2, K22.6, K22.8, K25.0, K25.2, K25.4, K25.6, K26.0, K26.2, K26.4, K26.6, K27.0, K27.2,

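### The one-day gap for recurrent IS/SE counts a same-episode readmission coded I63 or I74 as a new event, and no sensitivity analysis varies it

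*Protocol*

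**What the plan says.** Section 8.2 names the outcome as a secondary objective: "To describe the risk of recurrent IS/SE as combined effectiveness outcome", in the overall population and in patients with renal impairment.

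Section 9.3.2 identifies IS and SE from the primary hospital discharge diagnosis and dates them at admission: "The event date will be set to the admission date of the respective hospitalization". Annex 3 gives the codes: "Ischemic stroke (IS): ICD-GM: I63", and I74 for SE. The same section then sets one recurrence rule for hospitalizations in general and for IS/SE. A stay is a recurrent event "if there was at least one day between hospital discharge date of the prior and the admission date of the respective hospitalization".

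Section 9.7.2 analyses recurrent events by the mean cumulative function (MCF) and by the Wei-Lin-Weissfeld model with event-specific effects, in the unadjusted, matched and weighted populations.

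Section 9.9 accepts that "case validation is not possible and outcome misclassification cannot be ruled out". Its only safeguard against false-positive events is the restriction to primary diagnoses. Section 9.7.3 lists three sensitivity analyses: stockpiling, exclusion of patients with a prior event, and the personalized phenprocoumon dose.

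**The concern.** The rule serves two different kinds of outcome. In all-cause hospitalization the admission is itself the event, so a one-day gap is enough to separate two of them. In recurrent IS/SE the event is a new stroke or embolism, and the admission is only its marker. A patient discharged on day 10 and readmitted on day 13 for the same infarct, again with I63 as primary diagnosis, is recorded as having had two strokes.

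At stake is the meaning of a named effectiveness outcome. Each such readmission adds one event to the MCF and supplies an event to the second- or later-event estimates. If the chance of such a readmission per first event is the same in all groups, the false recurrences are proportional to the first events, and the recurrent result drifts towards repeating the first-event result. If that chance differs between groups, for example with the severity of the first event, the comparison is biased in a direction that the protocol does not determine.

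**Working it through.** **Logic of the rule**

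1. The wording can mean that admission on the next calendar day already counts, or that one full free day is needed. The first reading merges same-day transfers only; the second also merges next-day admissions. Under both, a readmission three days after discharge is a new event.
2. A new IS/SE event needs a primary code I63 or I74. Readmissions coded otherwise are not counted. Two stays for one infarct that both carry I63 as primary diagnosis pass the test equally, so the restriction in 9.9 cannot tell them apart.
3. No sensitivity analysis in 9.7.3 changes the gap, and none covers recurrent IS/SE.
4. Follow-up for a time-to-first analysis ends at the first event: "patients will be followed from the index date until the first diagnosis of the respective outcome event". The rule therefore cannot alter time-to-first IS/SE. Section 9.7.2 also notes that the first-event estimate of the Wei-Lin-Weissfeld model equals the Cox estimate. Only the MCF and the second- and later-event estimates are affected.

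**Scale**

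The protocol gives no expected count for recurrent IS/SE, so there is no such figure to reproduce. The expected IS/SE events in Table 3 (users × rate × 1 year) do reproduce:

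- phenprocoumon 35,400 × 0.025 = 885 (stated 885)
- apixaban 16,800 × 0.027 = 453.6 (454)
- rivaroxaban 30,200 × 0.022 = 664.4 (664)
- edoxaban 1,600 × 0.022 = 35.2 (35)
- total of the stated figures: 2,038

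*Illustration A, phenprocoumon only.* All of these inputs are assumed: same-episode readmission with I63/I74 after 1% to 10% of first events; on average 0.5 year of follow-up after a first event; true recurrence at 2.5 to 10 per 100 person-years.

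- False: 885 × 0.01 = 8.85; 885 × 0.10 = 88.5
- True: 885 × 0.5 × 0.025 = 11.06; 885 × 0.5 × 0.10 = 44.25
- Lowest false share: 8.85 / (8.85 + 44.25) = 17%
- Highest false share: 88.5 / (88.5 + 11.06) = 89%
- With 10% readmission and the higher recurrence rate: 88.5 / (88.5 + 44.25) = 67%

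*Illustration B, all four groups.* Assumed: true recurrence in 3% to 10% of the 2,038 patients, same-episode readmission in 1% to 10%.

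- True: 61 to 204. False: 20 to 204
- Lowest false share: 1 / (1 + 10) = 9%. Highest: 10 / (10 + 3) = 77%. At 5% and 5%: 50%

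*Effect on the MCF.* The MCF also counts first events, so its relative inflation is smaller. With the counts of illustration A, as a rough ratio, it is 8.85 / (885 + 44.25) = 1% to 88.5 / (885 + 11.06) = 10%. The second- and later-event estimates carry the larger shares above.

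**The case against.** **The primary endpoint.** A reader might infer that the rule puts false first events into the primary IS/SE composite, because a patient who starts treatment soon after a stroke could be readmitted for it. The protocol does not support this as a consequence of the rule, which defines recurrence only. The separate issue of a stroke before the index date is partly covered. The second sensitivity analysis in 9.7.3 repeats the Cox regression for IS, SE and severe IS without patients who had a prior event in the baseline period. Prior IS or transient ischemic attack is also a listed covariate, and prior IS or SE is a subgroup. What remains is a small gap: that sensitivity analysis does not list the combined IS/SE endpoint, which is the primary effectiveness outcome.

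**The size.** A reader might also infer that the recurrent result would mostly reflect care pathways. The protocol gives neither a readmission nor a recurrence rate, nor does it say how often one stroke leads to several stays with the same primary code. The 89% end also uses a recurrence rate of 2.5 per 100 person-years, which is Table 3's rate for all phenprocoumon users and so allows no extra risk after a first stroke. This objection stands. Only the direction of the count is established.

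**Limited reach.** The same rule applies in every group, the outcome is secondary, and the protocol's abstract calls p-values and confidence intervals non-confirmatory. This lowers the stakes. It does not make a same-episode readmission a new stroke, and equal application does not ensure equal readmission rates.

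**The interval.** Nothing in the protocol establishes 30 days for this purpose. Section 9.3.2 uses 30 days after discharge to link a death to a bleeding stay, which is a different question. A longer interval also drops true early recurrences. Both points are right, and they are why both versions should be reported.

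**Conclusion.** The point holds for the secondary recurrent IS/SE outcome. The one-day gap over-counts recurrences whenever a same-episode readmission again has I63 or I74 as primary diagnosis, and nothing else in the protocol offsets or tests this.

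The size cannot be derived from the protocol. Under the assumed rates, artefacts are about 9% to 89% of counted recurrences, and the MCF is inflated by about 1% to 10%. The effect on between-group estimates may go either way. The rule is sound for all-cause hospitalization and does not touch time-to-first IS/SE.

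**What to change.** 1. In 9.3.2, keep the one-day rule for all-cause hospitalization, and say whether a next-day admission satisfies it.
2. For recurrent IS/SE within follow-up, pre-specify a longer minimum interval between discharge from the previous I63/I74 stay and the next such admission. Thirty days is one possible convention; the protocol gives no basis for a particular figure, so the choice should be justified. Report the one-day version alongside it.
3. Do not extend the interval to stays before the index date. That would redefine the primary outcome and drop true early on-treatment events. Instead, add the combined IS/SE endpoint to the sensitivity analysis in 9.7.3 that excludes patients with a prior event in the baseline period.

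The cost is a sentence in 9.3.2, one extra run of the recurrent IS/SE analyses, and one more outcome in an existing sensitivity analysis, all on data already held. The downside is that true recurrences inside the interval are missed in the longer-interval version; they remain visible in the one-day version.

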9.3.3 Covariate definition

All demographic and clinical characteristics will be assessed based on primary and secondary hospital diagnoses and verified ambulatory diagnoses (ICD-10 GM codes), OPS codes, EBM codes and ATC codes as defined in Annex 3: Additional information. Unless otherwise mentioned, all information on covariates will be collected in the baseline period., i.e. in the 365 days prior to the index date). The assessment date for hospital diagnoses will be the admission date of the respective hospitalization and for ambulatory diagnoses the date of the first encounter with the diagnosing physician in the respective quarter (as ambulatory diagnoses are available on a quarterly basis only). Data derived from OPS codes and EBM codes will be assessed on the exact date.

Demographic characteristics

- Gender at index date
- Age at index date
- Age at index date categorized: 18–39, 40–44, 45–49, ..., 85-89, 90+ years

Clinical characteristics

- CHADS₂ score
- CHA₂DS₂-VASc score
- modified HAS-BLED score (the INR will not be included in the calculation of the score because this information is not available in the InGef database, end-stage renal disease will not be considered as these patients will be excluded from the analysis)
- Comorbidities
 - o Alcohol abuse
 - o Anemia
 - Aortic plaque
 - o Anemia
 - Coronary heart disease
 - Angina pectoris
 - Myocardial infarction
 - Acute ischemic heart diseases
 - Chronic ischemic heart disease
 - Coronary artery bypass graft(s)
 - Percutaneous coronary intervention
 - o Dementia
 - o Depression
 - o Diabetes mellitus
 - o Drug abuse
 - o Gastric or peptic ulcer disease/diseases of gastrointestinal tract
 - o Heart failure
 - History of major bleeding (hospitalization only)
 - o Hypertension
 - Hypothyroidism

- o Inflammatory bowel disease
- IS or transient ischemic attack
- Other cerebrovascular disease
- o Liver disease
- o Hyperlipidemia
- o Volume depletion
- Other metabolic disorders
- o Obesity
- Peripheral arterial disease
- o Psychosis
- o Pulmonary disease
- o Rheumatoid arthritis/collagen vascular disease
- Tobacco abuse
- o Other vascular disease
- Malignant cancer (except non-melanoma skin cancer)
- Comedications
 - o Angiotensin-converting enzyme inhibitors or angiotensin-receptor blockers
 - o Antiarrhythmics
 - o Antidepressants
 - o Antiplatelets
 - Antiulcer drugs (except proton-pump inhibitors)
 - o Calcium channel blockers
 - o Diabetes drugs
 - o Diuretics
 - o Erythropoietin-simulating agents
 - o Estrogens
 - o Lipid modifying agents
 - Non-steroidal anti-inflammatory drugs
 - o Proton-pump inhibitors
- Other indicators of overall health status

- Number of hospitalizations
- Number of different medications used (based on 7 digit ATC codes)
- o Number of ambulatory physician visits

Others

- Year of cohort entry
- Duration of follow-up in days
- Type of cohort exit (end of study period, switch, discontinuation, death, etc.)

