9.7.2 Main analysis

Analyses will be conducted in line with good statistical practices. Models will use confounding factors to adjust for group differences. However, unmeasured confounding and resulting confounding bias affecting point estimates, confidence intervals and any p-values in the treatment group comparisons may remain.

In a first step, Cox proportional hazards regression models will be applied in in each treatment group compared to phenprocoumon (reference) to estimate crude and confounder adjusted hazard ratios (HRs) of the above mentioned outcomes as well as treatment discontinuation (persistence) with accompanying 95% confidence intervals and *p*-values. Persistence (risk of non-persistence) will also be calculated separately for specific time points of interest (months 3, 6, 9, 12, 18 and 24). In the analysis of reduced vs. standard dose of NOACs, the standard dose will be used as reference. Kaplan-Meier cumulative incidence plots will be generated to characterize risk of outcome events of interest over time.

Information on confounding factors which are planned to be included in the models as well as in the estimation of the propensity score can be found in section 9.3.3.

In a second step, we will use the stabilized inverse probability of treatment weighting (IPTW) approach based on the propensity score to adjust for potential confounding resulting from imbalances in the baseline characteristics of different treatment groups. The objective of IPTW

based analysis is to create a weighted sample, for which the distribution of possible confounding variables is approximately the same between comparison groups (12,13). The propensity score is defined as the patient's probability to receive a treatment under investigation (i.e. phenprocoumon for main analyses and standard dose for the analyses of reduced vs. standard dose of NOACs) given a set of known patient's baseline characteristics. Propensity scores will be calculated using multiple logistic regression on a relevant set of patient characteristics listed in section 9.3.1 for each 1:1 comparison separately, e.g. rivaroxaban vs. phenprocoumon, rivaroxaban 15 mg vs. rivaroxaban 20 mg etc.

Let Z be an indicator variable relating to the treatment received by a patient, Z = 1 for an active treatment (e.g. rivaroxaban), Z = 0 for a control treatment (warfarin), and let X denote a vector of observed patient baseline characteristics. Then the propensity score is e = P(Z = 1|X). The inverse

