K27.4, K27.6, K28.0, K28.2, K28.4, K28.6, K29.0, K62.5, K66.1 K92.0, K92.1. K92.2, M25.0, N02, N42.1, N83.6, N85.7, N89.7, N93.0, N93.8, N93.9, N95.0, R04.0, R04.1, R04.2, R04.8, R04.9, R23.3, R31, R58, S06.4, S06.5, S06.6, S06.8

Section 9.3.3. Covariate definition

Operational definition of CHA2DS2-VASc Score:

Conditions	ICD-10 GM code	Assigned weights
Hypertension	I10 – I15, I67.4	1
Diabetes mellitus	E10 – E14	1
Heart failure	I11.0, I13.0, I13.2, I25.5, I42, I43, I50, I09.9	1
Age between 65 and 74 years		1
Vascular disease (previous MI, peripheral arterial disease or aortic plaque)	I21 – I23, I25.2, I70.0, I70.2 – I70.9, I71, I73.9	1
Stroke or TIA	G45.0 – G45.2, G45.4 – G45.9, I63, I69.3, I69.4, I64	2
Age \geq 75 years		2
Female sex		1

Operational definition of CHADS₂ Score:

Conditions	ICD-10 GM code	Assigned weights
Hypertension	I10 – I15, I67.4	1
Diabetes mellitus	E10 – E14	1
Heart failure	I11.0, I13.0, I13.2, I25.5, I42, I43, I50, I09.9	1
Stroke or TIA	G45.0 – G45.2, G45.4 – G45.9, I63, I69.3, I69.4, I64	2

Age ≥ 75	years
---------------	-------

1

Operational definition of modified HAS-BLED Score:

Criteria	ICD-10 GM / ATC /OPS code	Assigned weights
Hypertension	I10 – I15, I67.4	1
Liver or renal disease	B18.0, B18.1, B18.2, I85, K70.0, K70.2, K70.3, K70.4, K70.9, K72.1, K73, K74, K75.4, K75.8, K76.0, K76.6, K76.9, Z94.4, D63.1, E10.2, E11.2, E13.2, I12, I13, N02, N03, N04, N05, N07, N08, N14, N18.1-N18.4, N18.9, N19, Q61	1
Stroke history	I63, I69.3, I69.4, I64	1
Major bleeding event	OPS: 8800 ICD-GM: D62, H21.0, H31.3, H35.6, H43.1, H45.0, I32.1, I60 - I62, J94.2, M25.0, S06.4, S06.5, S06.6, S06.8	1
Alcohol abuse	F10	1
Non-steroidal anti-inflammatory drugs or antiplatelet	B01AC, M01A*	1
Age >65		1

Operational definition of claims based frailty indicator (10):

Criteria	ICD-10 GM / ATC /OPS code	Assigned weights
Impaired mobility	U50, Z99.3	1
Depression	F31, F32 – F34, F39, F43.1, F43.2,	1
Congestive heart failure	I11.0, I13.0, I13.2, I25.5, I42, I43, I50	
Parkinson's disease	G20-G22	

White race (yes vs. no)	N/A	
Arthritis (any type)	M05, M06, M08, L90.0, L94.0, L94.1, L94.3, M32 – M35, M45, M46, M48, M49	
Cognitive impairment	F01 – F05, F06.0, F06.7, F06.8, F07.0, F07.8, F09, G30, G31.0, G31.1, G31.8, R41	
Charlson comorbidity index (>0, 0)	As defined above	
Stroke	I60-I64, I69.0-4	1
Paranoia	F06.0, F06.2, F20, F22-F29, F32.3, F33.3, F44.8	
Chronic skin ulcer	170.24, 170.25, 183.0, 183.2, 187.21, L89, L97	
Male (yes vs. no)		

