Skin and soft tissue infection	L00-L06	
Mycoses	B35-B45	
Pneumonia	J10.0, J11.0, J12-J18	
Age (in 5 year categories)		
Hospital admission in past 6 months		
Gout or other crystal-induced arthropathy	M10, M11	1
Falls	N/A	1
Muscoskeletal problems	G45, M12-M14, M24, M25, M36, M43, M46, M47.1, M47.8, M50-M54, M67.8, M80, M81. M84.3, M84.4, M96.1, R26.2, R29.8, Z87.3	
Urinary tract infection	N10, N30, N34, N39.0	1

• Alcohol abuse:

ICD-GM: F10

BAYER E R

- Anemia: ICD-GM: D50 – D53, D63, D64.9
- Aortic plaque: ICD-GM: I70.0
- Coronary heart disease
 - Angina pectoris:
 - ICD-GM: I20
 - o Myocardial infarction:
 - ICD-GM: I21 I23, I25.2
 - Acute ischemic heart diseases:
 - ICD-GM: I24
 - Chronic ischemic heart disease:
 - ICD-GM: I25 (excl. I25.2)
 - Coronary artery bypass graft(s) :
 - ICD-GM: Z95.1
 - OPS: 5361, 5362
 - o Percutaneous coronary intervention:
 - OPS: 8837
- Dementia: ICD-GM: F01 – F03, G30, G31.0
- Depression:
 - ICD-GM: F31, F32 F34, F39, F43,1, F43.2
- Diabetes mellitus: ICD-GM: E10 - E14
- Drug abuse: ICD-GM: F11 – F19 (excl. F17.2)
- Gastric or peptic ulcer disease/diseases of gastrointestinal tract: ICD-GM: K21, K25.4 – K25.9, K26.4 – K26.9, K27.4 – K27.9, K28.4 – K28.9, K29, K30, K64
- Heart failure: ICD-GM: I11.0, I13.0, I13.2, I25.5, I42, I43, I50
- History of major bleeding (hospitalization only): OPS: 8800

ICD-GM: D62, H21.0, H31.3, H35.6, H43.1, H45.0, I32.1, I60 - I62, J94.2, M25.0, S06.4, S06.5, S06.6, S06.8

- Hypertension: ICD-GM: 110 - 115, 167.4
- Hypothyroidism: ICD-GM: E00, E01.8, E02, E03, E89.0
- Inflammatory bowel disease: ICD-GM: K51, K52
- Ischemic stroke or transient ischemic attack:
 - ICD-GM: G45.0 G45.2, G45.4 G45.9, I63, I69.3, I69.4
- Systemic embolism:
 - ICD-GM: I74
- Other cerebrovascular disease: ICD-GM: I64 - I69 (excl. I69.3, I69.4)
- Liver disease:

ICD-GM: B18.0, B18.1, B18.2, I85, K70.0, K70.2, K70.3, K70.4, K70.9, K72.1, K73, K74, K75.4, K75.8, K76.0, K76.6, K76.9, Z94.4

- Hyperlipidemia: ICD-GM: E78.0 – E78.5
- Volume depletion:

ICD-GM: E86

- Other metabolic disorders: ICD-GM: E87
- Obesity:

ICD-GM: E66

- Peripheral artery disease:
 - ICD-GM: I70.2 I70.9, I71, I73.9
- Psychosis:

ICD-GM: F20, F22 – F25, F28, F29 – F31, F32.3 – F32.5, F33.3, F33.4, F34.8, F34.9, F39, F44.8

- Pulmonary disease: ICD-GM: I27, I28.9, J44
- Rheumatoid arthritis/collagen vascular disease:

ICD-GM: M05, M06, M08, L90.0, L94.0, L94.1, L94.3, M32 - M35, M45, M46, M48, M49

• Renal impairment:

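### Prior stroke is adjusted for without any timing, so stroke recency is uncontrolled in the primary IS/SE contrasts and may leave residual confounding of unknown size and direction

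*Protocol*

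**What the plan says.** Section 9.3.3 sets the look-back: "Unless otherwise mentioned, all information on covariates will be collected in the baseline period". Its comorbidity list has a single entry for prior stroke, "IS or transient ischemic attack". Annex 3 gives its codes as "ICD-GM: G45.0 G45.2, G45.4 G45.9, I63, I69.3, I69.4", so TIA, acute ischemic stroke and sequelae share one indicator. Hospital diagnoses (primary or secondary) and verified ambulatory diagnoses count alike.

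Prior stroke also enters through three scores in the same list. CHADS2 and CHA2DS2-VASc use "G45.0 – G45.2, G45.4 – G45.9, I63, I69.3, I69.4, I64" with weight 2. The modified HAS-BLED item "Stroke history" uses I63, I69.3, I69.4 and I64 with weight 1, without TIA.

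Timing is known for inpatient events: "The assessment date for hospital diagnoses will be the admission date of the respective hospitalization". Section 9.7.2 points to 9.3.3 for "Information on confounding factors which are planned to be included in the models as well as in the estimation of the propensity score", so the list feeds both the Cox models and the propensity scores. Balance is judged by an absolute standardized mean difference (SMD) of 0.1 or less.

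Section 9.2.3 has no exclusion for a very recent stroke. Section 9.3.4 plans a prior IS/TIA/SE subgroup, based on the same 12-month window. Section 9.7.3 plans a Cox analysis that excludes patients with prior events for IS, SE and severe IS, among others. The combined IS/SE endpoint is not in that list.

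**The concern.** The short-term risk of a further IS/SE may well depend on how recent the last stroke was, and so may the choice between a NOAC and phenprocoumon. A covariate that covers 12 months and three kinds of code cannot separate the two situations. After weighting or matching, the arms can agree on the share of patients with any stroke or TIA code and still differ in the share who have just left hospital after a stroke. The contrast at stake is the primary effectiveness one: IS/SE in patients with renal impairment, each NOAC against phenprocoumon. The effects in view are modest. The earlier study in the same database, cited in section 7, reports stroke/SE hazard ratios of 0.77 for apixaban and 0.86 for rivaroxaban.

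**Working it through.** **1. Does any planned covariate carry time since stroke?**

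| Where prior stroke enters | Acute IS (I63) | TIA | Sequelae (I69.3, I69.4) | Time since event |
|---|---|---|---|---|
| IS/TIA covariate | yes | yes | yes | no |
| CHADS2, CHA2DS2-VASc | yes | yes | yes | no |
| Modified HAS-BLED | yes | no | yes | no |

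The HAS-BLED item makes TIA partly separable from stroke. Nothing makes recency separable. The number of hospitalizations is at best a weak proxy.

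**2. The plan's own figures.** The protocol has no figure for stroke recency. Table 3 in section 9.5 is used below for scale only. Its expected IS/SE events (users × rate × 1 year) reproduce:
- phenprocoumon 35,400 × 0.025 = 885
- apixaban 16,800 × 0.027 = 453.6 (stated 454)
- rivaroxaban 30,200 × 0.022 = 664.4 (stated 664)
- edoxaban 1,600 × 0.022 = 35.2 (stated 35)

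**3. Illustrative bias with the flag perfectly balanced.** All inputs here are assumptions. Let f be the share of patients flagged, s the recent share among flagged patients in an arm, and r the hazard ratio of recent against older flagged events. Flagged, not recent patients have twice the unflagged hazard. The mean relative hazard in an arm is

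h(s) = (1 − f) + f × [(1 − s) × 2 + s × 2r],

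and the spurious ratio is h(s₁)/h(s₀).

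Example with f = 0.15, r = 3, s = 0.40 against 0.20:
- h(0.40) = 0.85 + 0.15 × (1.2 + 2.4) = 1.39
- h(0.20) = 0.85 + 0.15 × (1.6 + 1.2) = 1.27
- ratio = 1.39/1.27 = 1.094

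Over f = 0.10 to 0.20 and r = 2 to 5:

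| Recent share, NOAC vs phenprocoumon | Spurious ratio |
|---|---|
| equal (30% vs 30%) | 1.00 |
| 30% vs 20% | 1.02 to 1.11 |
| 40% vs 20% | 1.04 to 1.21 |
| 50% vs 25% | 1.04 to 1.25 |
| 20% vs 40% | 0.97 to 0.83 |

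**4. Would the balance check reveal it?** In the example, recent stroke affects 0.15 × 0.40 = 6% of one arm and 0.15 × 0.20 = 3% of the other. On the proportion scale its SMD is 0.03/√[(0.06 × 0.94 + 0.03 × 0.97)/2] = 0.145, above the limit of 0.1. The flag's SMD is 0. A simulation of 2,000,000 patients with no treatment effect and stabilized weights on the flag alone agrees: flag SMD 0.00, recent-stroke SMD 0.14, weighted risk ratio 1.09. A recency indicator would therefore show an imbalance that the pooled flag hides.

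**5. Scale against precision.** ln(1.094) = 0.090.
- Overall population, rivaroxaban vs phenprocoumon: SE(log HR) ≈ √(1/664 + 1/885) = 0.051, so the example bias is about 0.090/0.051 = 1.8 SE.
- Renal impairment, the primary population: section 9.5 gives no expected events. With the 90 and 201 ischemic strokes of the earlier renal subgroup in section 7, SE ≈ √(1/90 + 1/201) = 0.127, so the same bias is about 0.7 SE.

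**The case against.** The strongest case against is that this is a modelling preference. The protocol contradicts nothing, accepts residual confounding in 9.7.2 and 9.9, bars confirmatory interpretation in the abstract, and promises a more detailed SAP. Two planned analyses also help: the stratum without prior events in 9.3.4, and the IS and SE exclusion analyses in 9.7.3. Both are largely free of the problem for events coded within 12 months.

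Much of this stands and limits the weight of the point. It does not remove it. The covariate is fixed by an explicit code list, so this is not detail left open. Section 9.9 attributes residual confounding to factors that claims data cannot measure adequately, and the admission date of a stroke is not such a factor. The exclusion analysis does not list the combined primary endpoint.

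Three stronger readings are tempting and are not supported.
- A reader might infer that prior stroke is controlled by one flag alone. It also enters through three scores, one of which leaves out TIA.
- A reader might infer that confounding does remain. That requires a different recency mix between arms, on which the protocol gives no figure. With equal mixes the bias is nil.
- A reader might point to the earlier renal subgroup in section 7. Its phenprocoumon arm had 201 strokes in about 5,934 person-years (3.39 per 100) under the shorter exposure definition and 75 more in the 5,293 person-years added by the longer one (1.42 per 100). This compares two exposure-time definitions within one arm. The added time is not ordered by time since index, depletion of susceptible patients or the supply rule could produce the same pattern, and the figures say nothing about prior stroke.

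**Conclusion.** The point holds in conditional form. As the protocol stands, prior stroke is adjusted for without timing, and the planned balance check cannot detect a difference in recency. If the mix of recent and older events differs between arms, some confounding stays in the primary IS/SE hazard ratios. Neither size nor sign can be derived from the protocol. The span of 0.83 to 1.25 illustrates what a balanced flag permits under assumed prevalence, recency shares and hazards, and its ends need large differences in recency between arms. It is not an estimate. The SAP, which is not at hand, may refine the covariate. This is a low-severity improvement, worth making because it costs little.

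**What to change.** In 9.3.3 and Annex 3, replace the pooled IS/TIA covariate by mutually exclusive indicators:
1. recent I63 hospitalization
2. older I63 hospitalization within the baseline period
3. TIA only
4. ambulatory-only or sequelae codes

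Fix the window for a recent event in advance. Date it by discharge, which Table 2 in section 9.4 lists as available, or by admission with a window that allows for length of stay. With a 30-day cut on admission, for example, a patient discharged a week before index after a stay of more than about three weeks would be classed as older.

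Use the indicators in the Cox models, the propensity scores and the balance tables. In 9.7.3, add combined IS/SE to the outcomes of the prior-event exclusion analysis.

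The cost is a few more binary covariates, which will be sparse in the edoxaban group (1,600 expected users), and one more Cox analysis. Ambulatory diagnoses are recorded by quarter only, so the fourth category will still mix recent and old events.
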